5.6 Test Drug Concentration

5.6.1 Pharmacokinetics

Pharmacokinetic samples will be collected at predose for all subjects to evaluate gilteritinib plasma concentrations as outlined in the Schedule of Assessments [[Table 1](#)].

For each sample, 2 mL of blood will be collected and processed.

Blood sampling, processing, storage and shipment instructions will be provided in the Laboratory Manual. Samples will be shipped to and analyzed by a sponsor-designated analytical laboratory. Please refer to the Laboratory Manual for more detailed information on this topic.

5.7 Other Measurements, Assessments or Methods

5.7.1 Blood and Buccal Swab Sample for Banked Pharmacogenomic Sample Analysis

Pharmacogenomic (PGx) research may be conducted in the future to analyze or determine genes of relevance to clinical response, pharmacokinetics and toxicity/safety issues. After enrollment, a whole blood and buccal swab sample will be collected for subjects who provide separate consent. Samples will be shipped to a sponsor-designated banking CRO.

Labels should uniquely identify each sample and contain at least:

- Protocol number (i.e., 2215-CL-1101)
- Subject number and
- Purpose and biological matrix (i.e., “biobanking,” “buccal sample”)

Details on sample collection, labeling, storage and shipment procedures will be provided in a separate Laboratory Manual. See [[Appendix 12.7 Adverse Events of Special Interest \(AESI\) for Atezolizumab](#)] for further details on the banking procedures.

5.7.2 Exploratory Biomarker

Bone marrow aspirate samples

Samples will be analyzed for MRD at any time point. Samples will be analyzed for FLT3 mutational status at screening/baseline and EOT, and may be analyzed for FLT3 mutational status at other time points. Samples may be analyzed for mutations in AML related genes and changes in proteins in relation to treatment effects at screening/baseline and EOT, and may be analyzed for mutations in AML related genes and changes in proteins in relation to treatment effects at other time points. Samples may be used for method development or validation of diagnostic assays related to study treatment.

Blood samples

Samples may be analyzed for MRD at any time point. Samples may be analyzed for FLT3 mutational status at screening/baseline and EOT, and may be analyzed for FLT3 mutational status at other time points. Samples may be analyzed for mutations in AML related genes and changes in proteins in relation to treatment effects at screening/baseline and EOT, and may be analyzed for mutations in AML related genes and changes in protein expression in relation to treatment effects at other time points.

Samples will be assessed for activation status of FLT3 and AXL, AML blast cell phenotyping and immunophenotyping for immune cell populations including, but not limited to, lymphocyte subsets, dendritic cells, natural killer cells, regulatory T cells and T lymphocyte subsets. Samples may be used for method development or validation of diagnostic assays related to study treatments.

Bone marrow/blood sampling, processing, storage and shipment instructions will be provided in the Laboratory Manual. Samples will be shipped to and analyzed by a sponsor-designated analytical laboratory. Samples will be stored for a period up to 15 years following study

database hard lock. Please refer to the Laboratory Manual for more detailed information on this topic.

5.7.3 Resource Utilization

Resource utilization in this study population will include analysis of data on hospitalization, blood transfusion, antibiotic IV infusions, medication for AEs and opioid usage. Details on hospitalizations and other relevant resource utilization will be collected at each study visit as indicated in the Schedule of Assessments [Table 1].

For each hospitalization, reason, admission and discharge dates, ward type (normal vs intensive care unit) will be recorded in the eCRF.

The following other resource utilization will be recorded in the eCRF: number of blood transfusions, number of units of each transfusion, number of antibiotic IV infusions, type of antibiotic, start/end dates of antibiotic treatment, type of medication for AEs, mode of administration of medication for AEs (oral, IV, etc.), start/end dates of medication for AEs, type of opioid medication, mode of administration of opioids, (oral, IV, etc.), start/end dates of opioids.

5.8 Total Amount of Blood

The total amount of blood collected for study assessments for each subject will vary depending on how long they stay on treatment.

At any time during the study, if any laboratory abnormalities are found for a subject, if results are needed before central laboratory results are available or for disease assessment, then additional blood may be drawn for monitoring.

Additional blood beyond standard monitoring that will be drawn for this study will include draws for eligibility assessment, serum chemistry, hematology, coagulation and pregnancy test at specific study defined time points, pharmacokinetics and bioanalytical sampling.

The maximum amount of blood collected for study specific assessments during the screening and cycle 1 period is approximately 42 mL.

The maximum amount of blood collected for study specific assessments in cycle 2 and beyond is approximately 36 mL per cycle.

6 DISCONTINUATION

6.1 Discontinuation of Individual Subject(s) From Study Treatment

A discontinuation from treatment is a subject who enrolled in the study and for whom both study treatments are permanently discontinued for any reason. If one treatment is discontinued due to toxicity, the subject may continue on the other as monotherapy until discontinuation criteria is met. The reason for discontinuation from study treatment must be documented in the subject's medical records.

All subjects who discontinue study treatment will remain in the study and must continue to be followed for protocol specific follow-up procedures as outlined in [Table 1 Schedule of Assessments]. The only exception to this is when the subject specifically withdraws consent for any further contact with him/her or persons previously authorized by the participant to provide this information.

All participants who discontinue study treatment are to be followed for up to 3 years after their EOT, death or the final analysis, whichever occurs first per [Table 1 Schedule of Assessments].

The subject is free to withdraw from the study treatment and/or study for any reason and at any time without giving reason for doing so and without penalty or prejudice. The investigator is also free to discontinue the subject from study treatment or to terminate a subject's involvement in the study at any time if the subject's clinical condition warrants it.

If a subject is discontinued from the study with an ongoing AE or an unresolved laboratory result that is significantly outside of the reference range, the investigator will attempt to provide follow-up until the condition stabilizes or no longer is clinically significant.

Subjects who meet any of the following criteria during the study will be withdrawn from study treatment:

- Subject declines further study participation (i.e., withdrawal of consent).
- Subject is non-compliant with protocol based on the investigator or medical monitor assessment.
- Subject is found to have significantly deviated from any one of the inclusion or exclusion criteria after enrollment (subjects having clinical benefit and no DLT may be kept in the study after discussion with the medical monitor).
- Subject develops an unacceptable study drug-related toxicity (DLT) or SAE requiring discontinuation of treatment.
- Subject receives any antileukemic therapy (including HSCT) other than the assigned treatment, with the exception of hydroxyurea up to 5 g daily for up to 2 weeks, prophylactic intrathecal chemotherapy or cranial irradiation.
- Subject has not achieved a PR or CRc, and in the opinion of the investigator, is no longer deriving clinical benefit after 6 cycles of therapy.
- Investigator/subinvestigator determines that the continuation of the study treatment will be detrimental to the subject.
- Subject is lost to follow-up despite reasonable efforts by the investigator to locate the subject.
- Female subject becomes pregnant.
- Death
- Subject is receiving gilteritinib, atezolizumab, or the combination of gilteritinib + atezolizumab and has progressive disease, recurrence under treatment, or no response, and in the opinion of the investigator the subject is no longer deriving clinical benefit.

Discontinuation criteria from long term follow-up for individual subjects:

- Subject declines further study participation (i.e., withdraws consent)
- Subject is lost to follow-up despite reasonable efforts by the investigator to locate the subject.
- More than 3 years has passed from the EOT Visit.
- Death

6.1.1 Lost to Follow Up

Every reasonable effort is to be made to contact any subject lost to follow up during the course of the study to complete study-related assessments, record outstanding data, and retrieve study drug.

6.2 Discontinuation of the Site

If an investigator intends to discontinue participation in the study, the investigator must immediately inform the sponsor.

6.3 Discontinuation of the Study

The sponsor may terminate this study prematurely, either in its entirety or at any study site, for reasonable cause provided that written notice is submitted in advance of the intended termination. Advance notice is not required if the study is stopped due to safety concerns. If the sponsor terminates the study for safety reasons, the sponsor will immediately notify the investigator and subsequently provide written instructions for study termination.

7 STATISTICAL METHODOLOGY

A statistical analysis plan (SAP) will be written to provide details of the analysis, along with specifications for tables, listings and figures to be produced. The SAP will be finalized before the database soft lock at the latest. Any changes from the analyses planned in SAP will be justified in the clinical study report.

In general, continuous data will be summarized with descriptive statistics (number of subjects, mean, SD, minimum, median and maximum), and frequency and percentage for categorical data.

Baseline will be defined as the last observation prior to first dose, unless otherwise specified.

Prior to database lock, a Final Review of Data and Tables, Listings and Figures Meeting will be held to allow a review of the clinical study data and to verify the data that will be used for analysis set classification. If required, consequences for the statistical analysis will be discussed and documented. A meeting to determine analysis set classifications may also be held prior to database lock.

7.1 Sample Size

This is an open-label, single arm study. No interim analysis and 1 final analysis are planned.

Phase 1

The sample size in phase 1 is based on 3+3 design and not based on power calculation.

Phase 2

Simon's 2-stage design [Simon, 1989] will be used in the study to evaluate the efficacy in terms of CRc rate for the selected combination dose level of gilteritinib and atezolizumab. The null hypothesis that the true CRc rate is 50% will be tested against a 1-sided alternative. In the first stage, the CRc of 22 subjects will be evaluated. If there are 11 or fewer subjects with CRc from these 22 subjects by the end of cycle 2, the study will be stopped. Otherwise, 27 additional subjects will be accrued for a total of 49 subjects evaluable for calculation of CRc rate. The null hypothesis will be rejected if 32 or more subjects with CRc are observed in the 49 subjects by the end of cycle 2. This design yields a 1-sided type I error rate of 0.025 and power of 80% when the true CRc rate is 70%. The sample size was calculated in East[®] Version 6.4.

Bayesian Posterior Probability for Safety Monitoring in Phase 2:

A Bayesian posterior probability will be used for safety monitoring during the whole treatment period. Subjects in phase 1 and phase 2 cohorts who complete the DLT observation period or experience DLTs will be included in the model-fitting process to provide the complete safety information. The DLT rate will be reviewed as the last subject of each cohort of 7 DLT-evaluable subjects completes the first treatment cycle. The estimated DLT rates based on the Bayesian beta-binomial model will be provided for safety monitoring in the dose expansion cohort. If the DLT rate for the expanded dose level is equal or higher than 20% with a posterior probability of 80%, then the enrollment to the expansion cohort will be paused and the safety will be reassessed by the DEC. If the reassessment warrants, enrollment to the expansion cohort may be continued at the current dose level or 1 lower dose level. Safety evaluation will be conducted separately for induction, consolidation and maintenance phases.

With a non-informative prior, Beta(1,1) distribution, the numbers of DLTs for each cohort of 7 DLT-evaluable subjects, which trigger the enrollment pause for toxicities review, are listed in the following [table](#):

DLT-evaluable Subjects	Number of DLTs
7	3
14	4
21	6
28	8
35	9
42	11
49	12

DLT: dose-limiting toxicity

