Caution is advised when considering the concomitant use of the following medications:

- Medications known to prolong QT or QTcF intervals.
- Strong inhibitors or inducers of P-glycoprotein and concomitant drugs that target serotonin 5HT_{2B}R are to be avoided with the exception of drugs that are considered absolutely essential for the care of the subject.
- Treatment with concomitant drugs that are strong inhibitors of CYP3A should be avoided with the exception of antibiotics, antifungals and antivirals that are used as standard of care to prevent or treat infections. If CYP3A inhibitors are used concomitantly, subjects should be closely monitored for AEs.

Precaution is advised in the use of gilteritinib (ASP2215) with concomitant drugs that are substrates of breast cancer resistance protein, since the transporter has been shown to be inhibited by gilteritinib (ASP2215) in in vitro studies.

Duration of Treatment:

Subjects will be treated until they no longer derive clinical benefit in the judgment of the treating physician, have unacceptable toxicity, undergo hematopoietic stem cell transplantation (HSCT), or meet 1 of the discontinuation criteria; whichever occurs first.

Definition of Dose Limiting Toxicity:

In phase 1, a DLT is defined as any of the following events that occur within the observation period (cycle 1/day 1 through cycle 1/day 28) and that is considered to be possibly or probably related to study regimen. In phase 2, the DLT observation period is the first treatment cycle (cycle 1/day 1 through cycle 1/day 28).

- Confirmed Hy's law case
- Any Grade ≥ 3 non-hematologic or extramedullary toxicity with the following exceptions:
 - Anorexia or fatigue
 - Grade 3 nausea and/or vomiting if not requiring tube feeding or TPN, or diarrhea if not requiring or prolonging hospitalization that can be managed to grade ≤ 2 with standard antiemetic or antidiarrheal medications used at prescribed dose within 7 days of onset
 - Grade 3 mucositis that resolved to grade ≤ 2 within 7 days of onset
 - Grade 3 fever with neutropenia, with or without infection*
 - Grade 3 infection*
 - Grade 3 infusion-related toxicity, if successfully managed and resolves within 72 hours.

*Toxicities are excluded only if the event is an expected direct complication of cytopenias due to the active underlying leukemia.

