6.2.1 Definition of DLT

In Phase 1, a DLT is defined as any of the following events that occur during the observation period (cycle 1/day 1 through cycle 1/day 28) and that is considered to be possibly or probably related to study regimen. In Phase 2, the DLT observation period is the first treatment cycle (cycle 1/day 1 through cycle 1/day 28).

- Confirmed Hy's law case
- Any Grade ≥ 3 non-hematologic or extramedullary toxicity with the following exceptions:
 - Anorexia or fatigue
 - Grade 3 nausea and/or vomiting if not requiring tube feeding or TPN, or diarrhea if not requiring or prolonging hospitalization that can be managed to grade ≤ 2 with standard antiemetic or antidiarrheal medications used at prescribed dose within 7 days of onset
 - Grade 3 mucositis that resolved to grade ≤ 2 within 7 days of onset
 - Grade 3 fever with neutropenia, with or without infection*
 - Grade 3 infection*
 - Grade 3 infusion-related toxicity, if successfully managed and resolves within 72 hours.

*Toxicities are excluded only if the event is an expected direct complication of cytopenias due to the active underlying leukemia.

Hematologic toxicity will not be considered as a DLT. However, prolonged myelosuppression defined as absolute neutrophil count (ANC) $\leq 0.5 \times 10^9/L$ for more than 21 days from the onset of severe neutropenia in the absence of evidence of active leukemia in the marrow or blood will be considered as a DLT.

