6.2.2 Definition of MTD

MTD is defined as the highest dose level where no more than one subject out of six eligible subjects has experienced DLT during the DLT observation period.

6.2.3 Bayesian Posterior Probability for Safety Monitoring in Phase 2

A Bayesian posterior probability will be used for safety monitoring during the whole treatment period. Subjects in phase 1 and phase 2 cohorts who complete the DLT observation period or experience DLTs will be included in the model-fitting process to provide the complete safety information. The estimated DLT rates based on the Bayesian beta-binomial model will be provided for safety monitoring in the dose expansion cohort. If the DLT rate for the expanded dose level is equal or higher than 25% with a posterior probability of 80%, then the enrollment to the expansion cohort will be paused and the safety will be reassessed by the DEC. If the reassessment warrants, enrollment to the expansion cohort may be continued at the current dose level or 1 lower dose level. Safety evaluation will be conducted separately for induction, consolidation and maintenance phases.

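### The Bayesian safety rule is said to cover the whole treatment period and three treatment phases, but it runs on cycle 1 DLTs only, so no prespecified study-level pausing rule is given after day 28

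*Protocol*

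**What the plan says.** The scope is stated in three places: the synopsis (Bayesian monitoring paragraph), Protocol 7.1 and SAP 6.2.3. Each opens with the claim "A Bayesian posterior probability will be used for safety monitoring during the whole treatment period" and closes with "Safety evaluation will be conducted separately for induction, consolidation and maintenance phases".

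The mechanics come between those two sentences:

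- **Data.** "Subjects in phase 1 and phase 2 cohorts who complete the DLT observation period or experience DLTs will be included in the model-fitting process".
- **Timing (protocol only).** "The DLT rate will be reviewed as the last subject of each cohort of 7 DLT-evaluable subjects completes the first treatment cycle".
- **Trigger.** In the protocol, enrollment pauses when the posterior probability of a DLT rate of at least 20% reaches 80%. The prior is Beta(1,1), and one table of counts runs from 7 to 49 evaluable subjects.

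The DLT definition fixes the window. The synopsis says "In phase 2, the DLT observation period is the first treatment cycle (cycle 1/day 1 through cycle 1/day 28", and SAP 6.2.1 repeats it.

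Protocol 2.2.1 and SAP 3.2.1 name three treatment periods. Neither document gives a start, an end or a cycle number for any of them.

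**The concern.** The opening and closing sentences promise more than the rule between them can deliver. An event on day 29 or later falls outside the phase 2 DLT window, so it has no way into the model. Nor is there a second event definition, threshold, denominator or review schedule that would give consolidation or maintenance a rule of their own.

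This is operative safety text. Treatment is open-ended (Protocol 5.1.1.1), and one of the two drugs is a checkpoint inhibitor. An investigator or ethics committee reading Protocol 7.1 would believe that a quantitative pausing rule stays in force throughout treatment. Protocol 10.1 says that no independent monitoring committee applies, and Protocol 10.2 ties DEC meetings to completion of the DLT observation period. A programmer asked to produce the posterior by phase could not do so from either document.

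**Working it through.** **Step 1. Reproduce the plan's table.** Inputs from Protocol 7.1: prior Beta(1,1), threshold 20%, posterior probability 80%. With x DLTs in n evaluable subjects the posterior is Beta(1+x, 1+n−x). The boundary is the smallest x for which P(p ≥ 0.20) ≥ 0.80.

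| n | Printed count | Recomputed | Posterior at that count | Posterior at one fewer |
|---|---|---|---|---|
| 7 | 3 | 3 | 0.944 | 0.797 |
| 14 | 4 | 4 | 0.836 | 0.648 |
| 21 | 6 | 6 | 0.867 | 0.733 |
| 28 | 8 | 8 | 0.892 | 0.790 |
| 35 | 9 | 9 | 0.832 | 0.716 |
| 42 | 11 | 11 | 0.865 | 0.771 |
| 49 | 12 | 12 | 0.814 | 0.711 |

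All seven agree. The table is one rule on one proportion, with nothing in it for a later period.

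**Step 2. Compare stated scope with the rule's inputs.**

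| Element | Stated scope | What the rule uses |
|---|---|---|
| Time | Whole treatment period | Cycle 1, days 1 to 28 |
| Event | Safety | DLT |
| Review point | Not stated for later cycles | Completion of cycle 1 by the last of each 7 subjects |
| Phases | Three, evaluated separately | One table; the periods are not delimited |

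**Step 3. What the rule responds to.** An exact binomial recursion over the seven looks gives the probability of ever pausing, by true cycle 1 DLT rate:

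| True cycle 1 DLT rate | Probability of ever pausing |
|---|---|
| 5% | 0.007 |
| 10% | 0.06 |
| 20% | 0.48 |
| 30% | 0.91 |
| 40% | 0.996 |

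Toxicity after day 28 changes none of these.

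**Step 4. Illustration with assumed rates (not in the documents).** Take a 5% cycle 1 DLT rate. Suppose that a fraction q of the remaining subjects has toxicity of DLT severity after day 28. The cumulative rate is 1 − 0.95 × (1 − q).

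| q | Cumulative rate | Pause probability, rule as written | Pause probability if the table counted later events too |
|---|---|---|---|
| 10% | 14.5% | 0.007 | 0.20 |
| 20% | 24.0% | 0.007 | 0.70 |
| 30% | 33.5% | 0.007 | 0.97 |

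The last column assumes that every later event is already known at each look. It is therefore an upper bound. It shows what the stated scope would imply and is not a proposed rule.

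**The case against.** The best defense is that the wording is loose and the rule is clear. The whole treatment period could mean the whole of phase 2 accrual, and the three-phase sentence speaks of safety evaluation, not of the posterior probability. SAP 7.5.1 does summarize treatment-emergent events by period, so a descriptive reading is available. Anyone implementing the table would find its event window and review points explicit in the protocol. This softens the point but does not remove it: the periods stay undefined on any reading, and no later event or boundary appears.

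A reader might infer that no toxicity rule of any kind exists after day 28. The documents do not support that. Rules for the individual subject continue: gilteritinib Table 5 (Protocol 5.1.2.1), atezolizumab Table 6 and the provisions for cycle 2 onward (5.1.3 and 5.1.3.1), withdrawal for toxicity (6.1), and the liver criteria in Appendix 12.5.

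A reader might also infer that a late signal could not halt enrollment. It could, by discretion. The sponsor monitors common serious events for changes in frequency (5.5.7), receives events of special interest within 24 hours (5.5.8), and may halt enrollment or stop the study for safety (5.5.12 and 6.3). Protocol 10.2 also leaves safety review time points to the DEC Plan, which may contain later reviews.

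Two further inferences should be resisted. The 12-week clauses in Table 6 concern failure to recover from an existing reaction, or failure to taper corticosteroids. They are not evidence of late onset. And the share of calendar time on treatment that falls after day 28 depends on an assumed treatment length and says nothing about the share of toxicity missed.

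**Conclusion.** The stated scope is wrong as written in all three places. The Bayesian rule is a cycle 1 DLT rule, and the documents contain no prespecified, quantitative, study-level rule that pauses enrollment for toxicity after day 28.

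The size is best put this way: the rule's chance of pausing depends on the cycle 1 DLT rate alone, so at an assumed 5% it stays at 0.007 whatever happens later. This rests on reading the phase 2 DLT window as the limit of what counts as a DLT, which is the plain sense of the synopsis and SAP 6.2.1. It also rests on the DEC Plan not being among the documents.

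The finding concerns a safeguard described but not present. A DLT rule confined to cycle 1 is coherent in itself, and nothing here shows that subjects go unprotected in later cycles.

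**What to change.** Reconcile the passages in the synopsis, Protocol 7.1 and SAP 6.2.3:

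1. Restate the Bayesian rule as monitoring DLTs in cycle 1.
2. Delete the three-phase sentence, or say that it refers to descriptive safety summaries by period and define the periods.

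If the sponsor does intend whole-period coverage, the text must instead define the later event, a denominator with adequate follow-up, the threshold, and where each period begins and ends. Applying the present table to later events at the present reviews would not serve. Those reviews fall as the newest subjects finish cycle 1, when they have no later follow-up, and others will have left for transplant, death or discontinuation, so late events would be undercounted.

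The minimum change costs only wording in two documents and alters no boundary or review. While SAP 6.2.3 is open, note a separate discrepancy: its threshold is 25% against the protocol's 20%, and it omits the prior, the review schedule and the table. At 25% the counts would be 3, 5, 7, 9, 11, 13 and 15, so the printed table fits only 20%.

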2.2 Study Design and Dose Rationale

2.2.1 Study Design

This is an open-label, single arm, phase 1/2 study to evaluate the safety and efficacy of combining gilteritinib with atezolizumab for subjects with relapsed or treatment refractory FLT3 mutated AML. This study will have 2 phases. Refer to [[Section V Flow Charts and Schedule of Assessments](#)] for details of design.

Phase 1:

The phase 1 portion of this study is a dose- escalation phase with a 3 + 3 design to establish the recommended phase 2 dose (RP2D) of gilteritinib given in combination with atezolizumab. Up to 12 subjects will be enrolled in cohorts of 3 to 6 subjects to determine the RP2D following the dose levels of the combination treatment outlined in the table below. Dose escalation decisions will be made based on DLTs that occur during the first cycle of treatment. A cycle is defined as 28 days. The treatment will consist of 3 distinct periods; remission induction, consolidation and maintenance.

The DLT observation period will be from cycle 1/day 1 through cycle 1/day 28. Evaluable subjects are defined as subjects who experience a DLT or in the absence of DLT, receive at least 23/28 doses of gilteritinib and at least 1/2 doses of atezolizumab. Subjects who are later discovered not to meet eligibility criteria or are not evaluable for DLT may be replaced.

Dose evaluation rules based on the 3 + 3 design and dose escalation rules are as follows:

Number of Subjects with DLT at the Given Dose During the DLT Observation Period	Escalation Decision Rules
0 of 3 or ≤ 1 of 6 subjects	Escalate and enter up to 3 subjects at the next dose level, if next dose level available. If at dose level 2, determine if RP2D.
1 of 3 subjects	Enter up to 3 subjects at the same dose level.
≥ 2 subjects	De-escalate or stop escalating.

DLT: dose limiting toxicity

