7.5 Analysis of Safety

All analysis of safety will be performed on the SAF, unless specified otherwise.

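### The phase 2 DLT pause rule is written for two different populations, and following its inclusion sentence can cancel a pause that the printed table calls for

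*Protocol*

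**What the plan says.** Protocol 7.1 describes a Bayesian beta-binomial model for the DLT rate in phase 2. Four statements in that section bear on who is counted.

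- Who enters the model: "Subjects in phase 1 and phase 2 cohorts who complete the DLT observation period or experience DLTs will be included in the model-fitting process". SAP 6.2.3 repeats this sentence.
- When the rate is reviewed: "The DLT rate will be reviewed as the last subject of each cohort of 7 DLT-evaluable subjects completes the first treatment cycle".
- What triggers a pause: "If the DLT rate for the expanded dose level is equal or higher than 20% with a posterior probability of 80" per cent, enrollment is paused and the Dose Evaluation Committee (DEC) reassesses safety.
- The limits: "With a non-informative prior, Beta(1,1) distribution", a table gives the numbers of DLTs "which trigger the enrollment pause for toxicities review": 3, 4, 6, 8, 9, 11 and 12 at 7, 14, 21, 28, 35, 42 and 49 DLT-evaluable subjects.

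Evaluable is defined only under the phase 1 heading of Protocol 2.2.1 (also in the synopsis and SAP 3.2.1): a subject who has a DLT or, without one, must "receive at least 23/28 doses of gilteritinib and at least 1/2 doses of atezolizumab".

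SAP 6.2.3 leaves out the review schedule, the prior and the table. It also changes the threshold: "If the DLT rate for the expanded dose level is equal or higher than 25% with a posterior probability of 80" per cent. Neither Protocol 7.2 nor SAP 5 defines a DLT analysis set, and SAP 7.5 describes no DLT summary, although DLTs are part of the primary endpoint (Protocol 2.3.1, SAP 6.2).

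**The concern.** Completing 28 days is not the same as taking the minimum number of doses. A DLT-free subject who reaches day 28 on too few doses enters the model by the inclusion sentence but is not a DLT-evaluable subject in the table. Such a subject adds to the denominator and nothing to the numerator, so the posterior probability falls.

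The dose question is similar. A beta-binomial model has no dose term, phase 1 may include up to three dose levels, and the inclusion sentence takes phase 1 subjects without saying at which dose. The trigger is about the expanded dose level only. If subjects from a different, better tolerated dose are pooled, the rate at the expanded dose is diluted.

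At stake is whether the DEC is called to review toxicity when the dose being expanded has reached the stated limit. Two statisticians following the same section could give the DEC different answers from the same data.

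**Working it through.** **Inputs.** Beta(1,1) prior, 20% threshold, 80% certainty and the printed limits (Protocol 7.1); dose minimum of 23 of 28 gilteritinib doses (Protocol 2.2.1); 3 + 3 outcomes (escalation table, Protocol 2.2.1).

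**Formula.** With x DLTs in n subjects the posterior is Beta(1 + x, 1 + n − x). Let P = Pr(rate ≥ 0.20). The limit is the smallest x with P ≥ 0.80.

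**Step 1: reproduce the table.** Columns 3 and 4 below show that the printed limit reaches 0.80 at every look and one DLT fewer does not. All seven rows reproduce.

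**Step 2: add under-dosed completers.** Keep x and raise n by k DLT-free subjects. Column 5 gives the smallest k that cancels the pause.

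**Step 3: pool another dose.** Add 0 DLTs in 3 or 1 in 6, the outcomes that permit escalation. An asterisk marks a lost pause.

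| n | Limit x | P at x | P at x − 1 | k that cancels (P) | Plus 0/3 | Plus 1/6 |
|---|---|---|---|---|---|---|
| 7 | 3 | 0.944 | 0.797 | 4 (0.795) | 0.839 | 0.870 |
| 14 | 4 | 0.836 | 0.648 | 1 (0.798) | 0.716* | 0.769* |
| 21 | 6 | 0.867 | 0.733 | 3 (0.780) | 0.780* | 0.818 |
| 28 | 8 | 0.892 | 0.790 | 4 (just below 0.800) | 0.825 | 0.854 |
| 35 | 9 | 0.832 | 0.716 | 2 (0.784) | 0.759* | 0.795* |
| 42 | 11 | 0.865 | 0.771 | 4 (0.783) | 0.805 | 0.834 |
| 49 | 12 | 0.814 | 0.711 | 1 (0.793) | 0.749* | 0.783* |

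**Step 4: pool a rejected dose.** With 2 DLTs in 3, the DLTs needed at the expanded dose become 1, 3, 5, 6, 8, 9, 11, fewer at every look. With 2 in 6 they become 2, 4, 5, 7, 9, 10, 12: fewer at 7, 21, 28 and 42, unchanged at 14, 35 and 49. Pooling then pauses sooner.

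**Step 5: chance of at least one pause over the seven looks** (exact binomial, independent subjects).

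| True rate at expanded dose | Printed table | 0/3 pooled | 1/6 pooled |
|---|---|---|---|
| 25% | 74.4% | 64.0% | 66.2% |
| 30% | 91.1% | 85.4% | 86.5% |

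**Step 6: can an under-dosed completer occur?** The definition allows 28 − 23 = 5 missed gilteritinib doses. Protocol Table 5 provides for interruption of up to 14 days for related grade 3 non-hematologic toxicity, and some grade 3 events, fatigue among them, are exempt from being DLTs. Six or more days off for such an event leaves at most 22 doses and no DLT.

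**Step 7: end of the table.** Phase 2 alone can reach 49. With 3 to 6 phase 1 subjects at the same dose the total could be 52 to 55, for which no row exists. The same formula gives 13 at 52 and 14 at 55.

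**Step 8: the SAP threshold.** At 25% the limits become 3, 5, 7, 9, 11, 13, 15, so the printed table matches only 20%. At a true rate of 30% the chance of ever pausing is 73.5% instead of 91.1%.

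**The case against.** The strongest reply is that the section can be read sensibly. The decision sentence names the expanded dose level, so a careful statistician would restrict the model to it, and the table heading shows that evaluable subjects are meant. The trigger only pauses enrollment for DEC review. Detailed set criteria are deferred to the Classification Specifications and review details to the DEC Plan, neither of which is available here. Most related grade 3 non-hematologic events that interrupt dosing are themselves DLTs and so enter the numerator.

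Much of this stands, and it rules out several stronger readings that a reader might infer.

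- **That the safety analysis set (SAF) is a third denominator for the pause rule.** SAP 7.5 says "All analysis of safety will be performed on the SAF, unless specified otherwise", and the monitoring text does specify otherwise. The SAF is only the default for a DLT summary that the SAP does not describe.
- **That other-dose subjects are certainly pooled.** Pooling is one reading of an inclusion sentence that conflicts with its trigger sentence, not a settled rule.
- **That even the first look is easily lost.** Turning 3/7 into 3/13 (0.698) needs 0 DLTs in 6 at another dose, an outer bound: the escalation table adds subjects four to six only after 1 of 3 has a DLT. The pause at 7 survives both 0/3 and 1/6.
- **That pooling always hides toxicity.** Step 4 shows the opposite after a rejected dose.
- **That the lost pauses apply equally under the SAP.** At 25%, 4/14 and 9/35 are not pauses to begin with.

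What does not stand is that the sensible reading makes correction unnecessary. The inclusion sentence is explicit, appears in both documents, and in the SAP is the only statement of who is counted.

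**Conclusion.** The point holds as a conflict between two populations for one safety rule, with an unstated dose restriction and a table that makes no allowance for phase 1 subjects. Its size varies by look: one under-dosed completer is enough at 14 and 49, two at 35, three at 21 and four at 7, 28 and 42. Pooling 0/3 cancels the pause at four of seven looks and pooling 1/6 at three. At a true DLT rate of 25% to 30%, pooling either result lowers the chance of ever pausing by about 5 to 10 percentage points. A rejected dose with 2 or more DLTs works the other way.

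The number of under-dosed completers and the other-dose results are assumptions, not data; the documents give no expected frequency. All lost-pause figures use the Protocol's 20% threshold. The conflict between 20% and 25% is separate and must be reconciled; this review does not say which value should stand.

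**What to change.** 1. Define one DLT-evaluable set in Protocol 7.2 and SAP 5, stated to apply to both phases. The only definition now in the documents is the one under the phase 1 heading; the sponsor should confirm that it carries over to phase 2.
2. Rewrite the inclusion sentence in Protocol 7.1 and SAP 6.2.3 so that the model uses DLT-evaluable subjects treated at the expanded dose level (RP2D), matching the trigger sentence.
3. State whether phase 1 subjects at that dose count toward the looks. If they do, extend the table past 49. If not, say that the table is for phase 2 subjects only.
4. Reconcile the 20% and 25% thresholds, and put the prior, review schedule and matching table into the SAP.
5. Add to SAP 7.5 a DLT rate by dose level on the DLT-evaluable set.

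The cost is wording in both documents and one output table. At 20%, the seven printed limits do not change. Compared with pooling all doses, pauses would come more often if the other dose had few DLTs and less often if it was rejected.
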